# 10b. Secondary Outcome(s)

Secondary outcome(s) include differences between the two arms in:

- Resting blood pressure
- Endothelial function
- Physical and cognitive functions
- Greater weight loss and lower drop-out rate at the end of the 2-week intervention

#### 11. STUDY PROCEDURES

The study will be conducted according to the following procedures.

# 11a. Recruitment of participants

Subjects will be enrolled via the weight loss clinical facilities of the Nutrition and Dietetics facilities of the Faculty of Medical School of the University Federico II of Naples, Italy. Eligible subjects at the first medical assessment visit will be provided with information about the study asked whether they want to enroll into the trial.

#### 11b. Randomisation

Participants will be randomised to one of the two interventions using a block-randomisation procedure. Blocks will consist of 5 participants per block and the randomisation sequence will be calculated using RandList for Windows.

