#### 6. STUDY DESIGN

This is a two-arm, open-label, parallel randomized clinical trial. Subjects will be either randomized to either caloric restriction plus beetroot juice (as a rich source of inorganic nitrate) or caloric restriction alone (control).

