#### 8. STUDY POPULATION

Study will be conducted in overweight and obese middle-aged and older men and women attending the weight loss clinical facilities of the Nutrition and Dietetics facilities of the Faculty of Medical School of the University Federico II of Naples, Italy. Subjects will attend a first medical assessment visits and if eligible subjects will be invited to enroll the study after being thoroughly explained the aims, objectives and safety of the study by one of the investigators. Subjects will have at least one day to decide whether they wish to enroll in the trial. In total 36 subjects will be recruited (18 per arm).

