Dietary Planning and Baseline Measurements (VISIT 2): After 7 days, participants will return to the research centre to obtain information on the dietary and lifestyle intervention and perform the baseline measurements. Participants will arrive early in the morning in fasting conditions. They will provide a urine and saliva sample and then resting energy expenditure will be measured. This will be followed by measurement of endothelial function and resting blood pressure. Body composition will then be assessed by bioelectrical impedance and bilateral hand grip strength will also be assessed. Subjects will then complete a series of questionnaires including assessment of cognitive function, dietary assessment and physical activity level. After these measurements participants will be provided with details about the weight loss interventions and, if allocated to the beetroot group, they will be given 14 bottles of beetroot juice. Subjects will start the weight loss intervention the day after the visit and continue for 14 days. They will return to the clinic in the morning of the 15th day for their final visit and complete the end of the study measurements.

**End Visit (VISIT 3):** Subjects will arrive early in the morning the day after they had consumed their 14th beetroot juice bottle. They will be in fasting conditions and measurements will be repeated in the same order as at baseline.

**Interventions:** Each participant will be invited to start each intervention at the end of the baseline visit and continue for 14 days until they will return to weight loss clinic for their final visit (15 day). 18 participants will be allocated to the weight loss plus beetroot juice and 18 participants to weight loss alone. The two interventions are described below.

- 1) Weight loss: A hypocaloric low fat diet will be prescribed to each participant. The caloric restriction will be calculated as 40% of total energy requirements and macronutrients composition will be of approximately: CHO= 55-60%, FAT= 20-25%, PRO= 15-20%. The amount of high nitrate food (ie. lettuce, rocket, cabbage, spinach, broccoli, etc) will be similar between diets. Participants will be asked to drink the same water during the two weeks intervention. Participants will be asked to not change their habitual physical activity level and alcohol and caffeinated drinks consumption during the trial.

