## 12. STATISTICAL CONSIDERATIONS AND DATA ANALYSIS

### 12a. Sample size and statistical power

The sample size calculation was performed using G-Power (version 3). The model selected for the study was a t test model for independent measures. The outcome for the calculation of sample size was difference in REE between intervention and control. A difference between intervention and control of 150 kcal/day (SD:  $\pm 150 \text{kcal/day}$ ). Power and significance levels were set at 0.80 and 0.05, respectively. Using these parameters we estimated a total sample size of 18 participants per group, i.e, 36 participants in total.

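### Blocks of 5 in a two-arm trial do not guarantee the 18-per-arm allocation that the protocol states

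*Protocol*

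**What the plan says.** Section 11b (Randomisation) gives the method, "Participants will be randomised to one of the two interventions using a block-randomisation procedure", and then the block size and software: "Blocks will consist of 5 participants per block and the randomisation sequence will be calculated using RandList for Windows". Section 6 describes the design: "This is a two-arm, open-label, parallel randomized clinical trial". Section 7 adds that there is one centre.

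The arm sizes appear in four places, and all agree. Section 8 plans 36 participants, 18 in each arm. Table 1 in section 11c lists 18 for each intervention. The Interventions text in section 11c states it as an allocation: "18 participants will be allocated to the weight loss plus beetroot juice and 18 participants to weight loss alone". Section 12a derives 18 per group from the power calculation.

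The protocol states no unequal ratio, no stratification, and no rule for how the five places in a block are divided between the arms.

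**The concern.** Permuted blocks are normally used to hold the arms at the intended ratio. For a 1:1 ratio, each block must contain the same number of places for each arm, and an odd block cannot. Two statements in the protocol therefore do not fit together: the block rule, and the 18-per-arm allocation that it is meant to deliver. Whoever generates the list must add a rule that the protocol does not contain, and different rules give different arm sizes. At stake are whether the allocation can be reproduced from the protocol and whether the arm sizes in the trial match those in the sample-size section.

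A second, separate matter is that the block size is constant and printed in the protocol of an open-label, single-centre trial. Someone who knows the earlier assignments could work out some of the later ones.

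**Working it through.** **Inputs.** Block size 5 and two arms (section 11b); 36 participants, 18 per arm (sections 8, 11c and 12a); difference 150 kcal/day and SD 150 kcal/day, so d = 150/150 = 1.0; power 0.80, alpha 0.05 and an independent-samples t test (section 12a). Sidedness is not stated, so I assume two-sided.

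**1. The protocol's own figure.** The normal approximation, n = 2(1.96 + 0.84)² / d², gives 15.7, so 16 per arm. The exact noncentral t calculation needs 17 per arm (power 0.807); 18 per arm gives 0.830. The stated 18 per group is therefore reproduced with a small margin.

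**2. Blocks against the total.** 5/2 is not a whole number, so the closest split of a block is 3:2. 36 = 7 × 5 + 1, so there are seven complete blocks and one participant in an eighth.

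**3. Same 3:2 composition in every block.** Seven blocks give 7 × 3 = 21 against 7 × 2 = 14. The 36th participant makes it 22:14 or 21:15. A split of 18:18 is impossible.

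**4. Majority arm drawn at random for each block (not stated).** One arm receives 2 × 7 = 14 participants, plus one for each block in which it holds the majority, plus possibly the 36th participant. Its size is 14 + Bin(8, ½).

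- P(18:18) = C(8,4)/2⁸ = 70/256 = 27%.
- P(19:17 either way) = 2 × 56/256 = 44%, so 71% of lists end at 18:18 or 19:17.
- P(difference of 4 or more) = 2 × (28 + 8 + 1)/256 = 74/256 = 29%.
- The range is 14:22 to 22:14.

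**5. Power at each split.** Exact t test on 34 degrees of freedom, with noncentrality d√(n₁n₂/(n₁+n₂)):

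| Split | n₁n₂/36 | Power |
|---|---|---|
| 18:18 | 9.00 | 0.830 |
| 19:17 | 8.97 | 0.829 |
| 20:16 | 8.89 | 0.825 |
| 21:15 | 8.75 | 0.820 |
| 22:14 | 8.56 | 0.811 |

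**6. Predictability.** An assignment is fully determined when the earlier ones in its block leave only one arm available. For a block with known composition of a and b places, the expected number of determined assignments is the mean length of the final run, a/(b+1) + b/(a+1).

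| Scheme, with sizes known | Expected determined | Share |
|---|---|---|
| Blocks of 5, fixed 3:2 | 3/3 + 2/4 = 1.5 of 5 | 30% |
| Blocks of 5, random majority | 2/4 = 0.5 of 5 | 10% |
| Blocks of 4 | 2/3 + 2/3 = 1.33 of 4 | 33% |
| Blocks of 6 | 3/4 + 3/4 = 1.5 of 6 | 25% |
| Three of 4 and four of 6, order also known | 3 × 1.33 + 4 × 1.5 = 10 of 36 | 28% |

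In the random-majority row, an assignment is determined only after one arm has three places. What is left is then the run of minority places at the end of the block.

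**The case against.** The strongest reply is that the mismatch has little practical effect. Unequal arms do not bias the comparison. Even the worst split considered keeps power above the target in section 12a ("Power and significance levels were set at 0.80 and 0.05, respectively"). If the majority arm varies, most lists end within one participant of 18 per arm. Many trials stop inside an incomplete block, and here that affects one participant. All of this stands, and it limits how serious the point is.

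A reader might also infer more than the protocol supports:

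- **That blocks of 5 can never give 18:18.** This is true only if all blocks share one 3:2 composition, and section 11b does not say so. With mixed directions, 18:18 can arise by chance. It can also be arranged: four 3:2 blocks and three 2:3 blocks give 18:17, and the 36th participant can go to the smaller arm. The supportable statement is that the rule does not guarantee 18 per arm. Splits of 4:1 or 5:0 have no basis in the text.
- **That the odd size makes assignments more predictable.** It does not. Blocks of 5 give 10% to 30% determined assignments, and fixed blocks of 4 or 6 give 33% and 25%. Predictability comes from a constant, disclosed size in an open-label trial.
- **That selection bias has been shown.** Section 11c places randomisation after the eligibility check and consent, and the protocol does not say who holds the list or sees earlier assignments. It is a risk only.

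The stray references to three interventions in section 11c do not explain the block size, since 5 is not divisible by 3 either. Whether the 5 is a typing error cannot be settled from the protocol.

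**Conclusion.** The point holds as an internal inconsistency. The block rule in section 11b does not deliver the 18-per-arm allocation stated in sections 8, 11c and 12a, and nothing in the protocol reconciles them. Depending on the unstated composition rule, the list ends at 21:15 or 22:14, or reaches 18:18 in 27% of cases.

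The cost in power is at most about 0.02 (0.830 − 0.811). That figure assumes a two-sided test, d = 1.0 and all 36 participants analysed. Drop-out would lower power under any split: 16 per arm gives 0.781 even when balanced. The point should therefore be corrected because the allocation is wrongly specified, not because the trial becomes underpowered.

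The disclosed fixed block size is a separate and lesser matter. It would apply to any constant size.

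**What to change.** Before the list is generated, replace the blocks of 5 in section 11b with even block sizes that sum to 36, and state the 1:1 ratio. A random-order mix of three blocks of 4 and four blocks of 6 works: 3 × 4 + 4 × 6 = 36, giving 3 × 2 + 4 × 3 = 18 per arm when all blocks are filled. Nine blocks of 4 or six of 6 also give 18:18, but with a constant size.

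For the lesser point, vary the block size and move the sizes to a restricted document that enrolling staff do not see. Withholding them matters, because the mix with known sizes and order would still leave 28% of assignments determined.

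If the list has not been made, the cost is a sentence or two in section 11b and a newly generated list. The protocol does not say whether enrolment has begun. If it has, the list should not simply be replaced; section 11b should record the block composition actually used, and the 18-per-arm statements should be reconciled with it.

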# 11c. Study procedure

The study is essentially divided in three phases: screening/baseline, intervention and end of study. A summary of the three phases is described in Table 1 which also includes a breakdown by time of the various measurements taken at each phase.

Table 1: STUDY TIMELINE				
Phases	Where	Details		
Visit 1 (Medical Assessment)	Clinic (Morning)	Check eligibility criteria, signing informed consent, anthropometric measurements and blood pressure.		
Agree to Participate and Eligible?				
No: Exclude from study				
Yes: Arrange appointment and randomise subject to intervention				
INTERVENTION 1: Weight loss plus Beetroot juice (1 per day) (18 participants)				
OR				
INTERVENTION 2: Weight loss alone (18 participants)				
	Clinic (Morning)	Saliva and urine sample		
Visit 2 (Dietary		Resting energy expenditure and endothelial function, BIA, hand-grip strength		
Planning and Baseline)		Cognitive function, dietary assessment and physical activity questionnaire		
		Explain study intervention (beetroot juice plus diet or diet only). Provide beetroot juice for 2 weeks		
	Clinic (Morning)	Saliva and urine sample		
Visit 3 (End visit after 14 days)		Resting energy expenditure and endothelial function, BIA, hand-grip strength		
		Cognitive function, dietary assessment and physical activity questionnaire		

**Medical Assessment (VISIT 1):** Participants will arrive in the morning for their first medical assessment visit. The aim of the study will be explained to potential, eligible participants by the investigators and, if they agree to participate in the study, they will be invited to sign the informed consent. Anthropometric (weight, height) and BP measurements will be taken to

confirm eligibility. Subjects will be subsequently randomized to one of the three interventions (weight loss plus nitrate or weight loss alone) and they will be invited to return after one week for their baseline visit. Resting energy expenditure will be calculated using the Fredrix's equation and multiplied by 1.5 to obtain an estimate of total energy expenditure. A dietary plan will be then designed to obtain a caloric restriction of 40% of baseline estimated total energy requirements.

Dietary Planning and Baseline Measurements (VISIT 2): After 7 days, participants will return to the research centre to obtain information on the dietary and lifestyle intervention and perform the baseline measurements. Participants will arrive early in the morning in fasting conditions. They will provide a urine and saliva sample and then resting energy expenditure will be measured. This will be followed by measurement of endothelial function and resting blood pressure. Body composition will then be assessed by bioelectrical impedance and bilateral hand grip strength will also be assessed. Subjects will then complete a series of questionnaires including assessment of cognitive function, dietary assessment and physical activity level. After these measurements participants will be provided with details about the weight loss interventions and, if allocated to the beetroot group, they will be given 14 bottles of beetroot juice. Subjects will start the weight loss intervention the day after the visit and continue for 14 days. They will return to the clinic in the morning of the 15th day for their final visit and complete the end of the study measurements.

**End Visit (VISIT 3):** Subjects will arrive early in the morning the day after they had consumed their 14th beetroot juice bottle. They will be in fasting conditions and measurements will be repeated in the same order as at baseline.

**Interventions:** Each participant will be invited to start each intervention at the end of the baseline visit and continue for 14 days until they will return to weight loss clinic for their final visit (15 day). 18 participants will be allocated to the weight loss plus beetroot juice and 18 participants to weight loss alone. The two interventions are described below.

- 1) Weight loss: A hypocaloric low fat diet will be prescribed to each participant. The caloric restriction will be calculated as 40% of total energy requirements and macronutrients composition will be of approximately: CHO= 55-60%, FAT= 20-25%, PRO= 15-20%. The amount of high nitrate food (ie. lettuce, rocket, cabbage, spinach, broccoli, etc) will be similar between diets. Participants will be asked to drink the same water during the two weeks intervention. Participants will be asked to not change their habitual physical activity level and alcohol and caffeinated drinks consumption during the trial.
- 2) Inorganic Nitrate Supplementation: Participants will be asked to drink 70ml of concentrated beet root juice per day corresponding to an average supplementation of 300-400mg of inorganic nitrate per day. This amount of nitrate intake is commonly observed in subjects with a high intake of fruit and vegetables (particularly leafy vegetables) and it is significantly lower than the nitrate intake that may be observed in vegetarian subjects. There is no established health risk associated with either this level of nitrate intake or with beet root juice supplementation. However, at the screening visit participants will be asked whether they have an aversion for beet root or beet root juice and they will be excluded if they report problems with the consumption of these products. Subjects will be invited to drink 70ml of beetroot juice in the morning. They will be provided with a sheet to record the time of the consumption and if they will experience any problem. Participants will be considered not compliant to the intervention if they will miss and/or not complete two or more

supplementation days. Participants will be provided with the specific amount of beetroot juice to be consumed during the 14-day period.

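### Randomisation at Visit 1 comes seven days before the REE, BIA and functional baseline at Visit 2, so the analysis baseline is post-randomisation in an open-label trial

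*Protocol*

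**What the plan says.** The order of events is stated consistently in the protocol.

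- **Design (section 6):** "This is a two-arm, open-label, parallel randomized clinical trial".
- **Randomisation (Table 1, section 11c):** once consent and eligibility are settled at Visit 1, the step is "Yes: Arrange appointment and randomise subject to intervention". The Visit 1 text agrees: "weight loss plus nitrate or weight loss alone) and they will be invited to return after one week for their baseline visit".
- **Measured before randomisation (Visit 1, section 11c):** "Anthropometric (weight, height) and BP measurements will be taken to" (the stated purpose is an eligibility check). REE at this visit is only calculated from an equation, to set the diet.
- **Baseline (Visit 2, section 11c):** the text reads "After 7 days, participants will return to the research centre to obtain information on the dietary and lifestyle intervention and perform the baseline measurements". This visit holds the first measured REE, BIA, endothelial function, grip strength and cognitive tests.
- **Intervention explained (Visit 2, section 11c):** the text reads "After these measurements participants will be provided with details about the weight loss interventions and, if allocated to the beetroot group, they will be given" (the supply of juice follows). Treatment comes later: "Subjects will start the weight loss intervention the day after the visit and continue for 14 days".
- **Analysis (section 12b):** repeated-measures general linear models, with and without adjustment for baseline, and a time x group interaction for between-group differences in change.
- **Time to decide (section 8):** "Subjects will have at least one day to decide whether they wish to enroll in the trial". Section 11c has consent signed and the participant randomised at the first visit.

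**The concern.** A baseline is safest when it is fixed before allocation, because allocation then cannot influence it. Here allocation precedes the baseline by a week, and no section says that participants or the people measuring them are kept unaware of it until the measurements are done. Two consequences follow.

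1. **Influence on the baseline.** Knowledge of the arm could change behaviour during the week or the conduct of the measurements. The exposed measures are mainly those that depend on effort, an observer or self-report: grip strength (best of three attempts), manual blood pressure, the cognitive tests and the diet and activity questionnaires. Section 12b uses the baseline both to form change and to adjust, so any arm-related shift reaches the estimated effect.
2. **Loss between randomisation and baseline.** A participant who leaves in that week has been randomised but has neither a baseline nor an end value for REE or BIA body composition, the primary outcomes in section 10a. If allocation is known, leaving could differ by arm. The analysis plan cannot recover measurements that were never taken.

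**Working it through.** **Sequence.** Visit 1: eligibility, consent, weight, height, blood pressure, randomisation. Seven days later, Visit 2: all baseline measurements, then explanation of the intervention and handing out of juice. Next day: treatment starts. The baseline is thus after randomisation and before treatment. Treatment itself cannot affect it; only knowledge of allocation, or withdrawal, can.

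**The plan's sample size.** Inputs from section 12a: difference 150 kcal/day, SD 150 kcal/day, power 0.80, significance level 0.05, independent t test. Sidedness is not stated; two-sided is assumed.

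- Standardised difference d = 150/150 = 1.0.
- Normal approximation: n per arm = 2(1.960 + 0.842)²/1.0² = 15.7, so 16.
- Noncentral t: 17 per arm, with power 0.807.
- The stated 18 per arm is close to both and has power 0.830. A one-sided test would need only 13 or 14, so two-sided is the better reading.

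The 18 follows from these four inputs alone; section 12a states no allowance for losses.

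**Effect of losses before Visit 2.** The loss rate is not given, so it is varied as an assumption. Noncentrality = d√(n₁n₂/(n₁+n₂)), degrees of freedom = n₁+n₂−2, two-sided 0.05, d = 1:

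| Analysable per arm | Noncentrality | Power |
|---|---|---|
| 18/18 | 3.000 | 0.830 |
| 17/17 | 2.915 | 0.807 |
| 18/16 | 2.910 | 0.806 |
| 17/16 | 2.871 | 0.794 |
| 18/15 | 2.860 | 0.791 |
| 16/16 | 2.828 | 0.781 |

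Two losses in total leave power just above 0.80; three take it just below.

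**Effect of a shifted baseline.** Let the mean baseline REE of one arm be shifted by δ because the arm is known, with end values unaffected.

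- Unadjusted change (end minus baseline): the between-arm difference moves by δ in size. For assumed δ = 15, 15/150 = 10% of the planned difference; for assumed δ = 30, 30/150 = 20%.
- Baseline-adjusted model: it moves by βδ, where β is the slope of end value on baseline. With β below 1, as is usual, the effect is smaller than the figures above.

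The protocol gives neither δ nor β. These figures show scale, not an expected bias.

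**The case against.** The strongest reply is that the protocol contains some protection and shows no actual bias.

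- **Who knows the arm at baseline.** A reader might infer from the open-label design that staff taking the baseline already know the allocation. The protocol does not say so. It does not state who measures, who holds the list or when the arm is disclosed, and it puts the explanation of the intervention and the juice after the Visit 2 measurements. What stands is that knowledge of the arm before baseline is possible and not excluded.
- **Instrument readings.** REE by indirect calorimetry and BIA are less open to assessor influence than grip strength or cognitive tests. This stands: the risk to the REE comparison is smaller than to several secondary outcomes.
- **Losses.** A reader might conclude that early losses cannot be analysed at all. That is too broad. Weight and blood pressure have Visit 1 values, and these participants can be counted as drop-outs, a secondary outcome in section 10b. If participants do not know their arm, such losses cost power rather than cause bias. Losses after Visit 2 are untouched by the fix.
- **Consent.** Moving randomisation might seem also to settle the conflict with section 8. It does not, because consent would still be signed at Visit 1.
- **Diet plan.** The protocol does not say whether the energy in the juice is counted in the plan drawn up at Visit 1. The 40% restriction itself is stated identically for both arms, so nothing written there requires the allocation.

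None of these replies gives a reason to randomise a week early.

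**Conclusion.** The point holds as an avoidable weakness in the visit schedule and should be fixed. The order of events is certain: it appears twice at Visit 1 and is confirmed at Visit 2. That the baseline is post-randomisation, and that anyone lost in the intervening week has no REE or BIA value, follows directly.

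The size is modest and conditional. A shift of 15 to 30 kcal/day and a loss of one or two participants per arm are assumptions. Under them the unadjusted effect would move by 10 to 20% of the planned difference, and power would be 0.807 or 0.781 against 0.830 at full size. The documents do not support a claim that the baseline is biased, that measurers are unblinded at that moment, or that the trial would be invalid as scheduled.

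**What to change.** - Randomise at the end of Visit 2, after all baseline measurements and before the intervention is explained and juice is handed out.
- Move the randomisation step in Table 1 and correct the Visit 1 text in section 11c to match. The caloric restriction can still be calculated at Visit 1. If the sponsor intends the dietary plan to differ by arm, the protocol should say so.
- Separately, reconcile section 11c, where consent is signed at the first visit, with the decision period of at least one day in section 8.

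The first change reorders steps already planned and needs no added visit, measurement or participant; the allocation sequence must simply be accessible at Visit 2. Anyone who withdraws before Visit 2 is then never randomised, so the 36 randomised participants all have a baseline. The sample size calculation is unchanged.

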#### Measurement Protocols

**Questionnaires:** Before and after the intervention participants will complete questionnaires on general health and lifestyle (IPAQ). In addition, participants' diet will be assessed using a standardized semi-quantitative food frequency questionnaire (FFQ). Subjects will also be administered a FFQ to evaluate nitrate intake. Cognitive tests (MMSE, TMT A and B) will also be administered at baseline and end of the study.

**Body composition:** Measurements will be performed at baseline and at the end of the 14-day interventions. Body weight, height and waist and upper-arm circumferences will be measured using standardised protocols.

**Resting blood pressure:** At baseline and end of the study resting blood pressure will be measured in triplicate using a manual BP monitor. Before the measurement participants will be invited to rest for at least 15 minutes. An appropriate cuff size will be utilised for the measurement of each subject which will be used for all other measurements of BP.

**Endothelial Function:** All the measurements will be undertaken in a temperature-controlled measurement room ( $\sim$ 23  $\pm$  1  $^{\circ}$ C). Each subject will be invited to lie supine for a 5 min rest period. A laser Doppler device will be used to measure microcirculatory blood flow.

**Hand-grip strength:** Hand-grip strength will be assessed in both arms at baseline and after intervention to measure the maximum isometric strength of the hand and forearm muscles. A lightweight and portable dynamometer will be used. The researcher will follow a specific protocol for the measurement of hand-grip strength (i.e. allowing one practice trial, and then record the best of three attempts with 30 seconds rest between each of these).

**Cognitive tests:** All participants will complete a short battery of cognitive tasks that includes Mini Mental State Examination and the Trail Making Test [TMT Parts A and B].

**Blood tests:** Fasting blood tests will be performed by each participant before and after the intervention.

**Urine and saliva collection:** A spot urine sample will be collected in the morning (not first void) at the beginning and end of the intervention for the measurement of nitrate excretion. Stimulated saliva sample will be collected in 1.5ml eppendorf tubes. Samples will be stored at -20°C until analyses

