**Dietary nitrate intake:** It is essential to modify the diet to restrict nitrate intake in order to standardise the effects of the diet across the three different interventions as well as to increase the likelihood of detecting unconfounded effects of physical activity and nitrate supplementation on the main outcomes. Human exposure to nitrate occurs primarily through the diet because nitrate occurs in both plants and water. Nitrate is used as a preservative in cured meat but fresh meat contains little nitrate. Fruit and grains have a small impact on dietary intake of nitrate and the dietary advice offered will be recent reports on nitrate content of foods. Therefore diets will be standardized for the consumption: vegetables with high nitrate content (rocket, spinach, cabbage, beet root), tomato based products such as (tomato

sauces, ketchup, tomato juice), cured meat, cured seafood and cured fish, mature cheese. A detailed dietary plan will be given to each participant.

**Compliance:** Compliance with the dietary interventions will be assessed by monitoring the dietary intake at baseline, after 7 days (telephone interview) and at end of the study (14th day). Assessment of compliance with the physical activity will be assessed by asking subjects to complete a physical activity questionnaire.

Compliance with the nitrate (beetroot juice) supplementation will be evaluated by the completion of a daily questionnaire asking each volunteer about the time of the consumption of the juice as well as evaluating the changes in urinary nitrate concentration during the intervention (baseline, day 14).

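### A record of problems during treatment is described for the juice arm only, so problem counts cannot be compared between arms or attributed to the juice

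*Protocol*

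**What the plan says.** Protocol section 11c describes the two interventions separately. Under the second, inorganic nitrate supplementation, it says of those drinking the juice: "They will be provided with a sheet to record the time of the consumption and if they will experience any problem". The first, the hypocaloric diet, carries instructions on diet, water, activity, alcohol and caffeine, but no sheet and no question about problems. The same 40% restriction applies to both arms.

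The Compliance paragraph under Measurement Protocols describes a daily record as a check on juice intake, through "completion of a daily questionnaire asking each volunteer about the time of the consumption of the juice".

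Three kinds of contact apply to both arms:
- Diet compliance is checked by "monitoring the dietary intake at baseline, after 7 days (telephone interview) and at end of the study (14th day" of treatment), with no restriction by arm.
- The Questionnaires paragraph says: "Before and after the intervention participants will complete questionnaires on general health and lifestyle (IPAQ").
- All participants attend a final visit: "They will return to the clinic in the morning of the 15 th day for their final visit".

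None of these is described as asking about problems during treatment.

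Section 6 states: "This is a two-arm, open-label, parallel randomized clinical trial". Section 10b lists among the secondary outcomes "Greater weight loss and lower drop-out rate at the end of the 2-week intervention". No tolerability or safety outcome is listed.

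**The concern.** The diet is common to both arms and can itself cause complaints. A juice participant who feels unwell on the diet has a daily sheet on which to say so. A control with the same complaint has no described place to record it. Counts from the sheet would then show complaints with juice and few or none without it, even if the juice caused none. Any descriptive statement on how well the juice was tolerated would inherit this bias. No later analysis plan can repair it, because the daily control data would not exist.

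There are two lesser consequences. Daily recording is a form of self-monitoring given to one arm, which could affect adherence; the protocol holds no data on whether it does. And the events that lead up to a withdrawal may be documented in one arm and not in the other, which limits interpretation of the reasons for drop-out.

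**Working it through.** **Step 1: what is recorded, by arm, in the text shown.**

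| Item | Juice + diet | Diet alone | Protocol location |
|---|---|---|---|
| 40% caloric restriction | yes | yes | 11c |
| Daily sheet with a problem entry | yes | not described | 11c, intervention 2 |
| Day-7 telephone interview (dietary intake) | yes | yes | Compliance |
| General health and lifestyle questionnaire, before and after | yes | yes | Questionnaires |
| Final visit, day 15 | yes | yes | 11c |
| Problem question at a common contact | not described | not described | none found |

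The asymmetry lies in the second row, and no other row offsets it.

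**Step 2: which outcomes it touches.** Drop-out can be counted from attendance at the day-15 visit, with 18 allocated per arm (section 8). The sheet enters neither numerator nor denominator. Resting energy expenditure and body composition are measured at the same visits by the same methods in both arms. What the sheet does touch is the frequency of problems and, possibly, the documented reasons for withdrawal.

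**Step 3: size of a false difference.** The protocol has no figure of its own to reproduce here. Let p be the true probability of a problem, equal in both arms, so that the juice has no effect. Assume the sheet captures every problem in the juice arm. Let s be the share of control problems that surfaces by other routes.

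- Expected number recorded, juice arm: 18p
- Expected number recorded, control arm: 18ps
- False risk difference: p - ps = p(1-s)

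The protocol states neither p nor s. The values below are assumptions that show the range.

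| p | s | Juice (of 18) | Control (of 18) | False risk difference |
|---|---|---|---|---|
| 0.10 | 0 | 1.8 | 0 | 0.10 |
| 0.10 | 0.5 | 1.8 | 0.9 | 0.05 |
| 0.20 | 0 | 3.6 | 0 | 0.20 |
| 0.20 | 0.5 | 3.6 | 1.8 | 0.10 |
| 0.40 | 0 | 7.2 | 0 | 0.40 |
| 0.40 | 0.5 | 7.2 | 3.6 | 0.20 |
| any | 1 | 18p | 18p | 0 |

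Under these assumptions the bias always runs against the juice. It vanishes only if control problems are captured in full.

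**Step 4: would it look like a significant difference?** By Fisher's exact test, two-sided, 4 of 18 against 0 of 18 gives p = 0.104, and 5 of 18 against 0 of 18 gives p = 0.045. With s = 0, a nominally significant excess therefore needs 5 or more in the juice arm. The binomial chance of that, for 18 participants, is 3% at a rate of 0.10, 28% at 0.20, 67% at 0.30 and 91% at 0.40. With s = 0.5, summing over both arms' binomial distributions, the chance of a significant excess in the juice arm is about 1%, 6%, 10% and 16% at the same rates. The answer thus depends almost wholly on two unknown inputs.

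**The case against.** The best counter-argument is that the sheet is a juice compliance tool. The same paragraph of section 11c uses similar wording about trouble consuming beetroot products, so the entry may be meant for difficulties with the juice, and controls would then have nothing to enter. This has force as a reading of intent. But the entry as worded is not limited to the juice, and a participant on a restricted diet would be within the instruction to write down a diet complaint.

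Second, no tolerability comparison is planned. This stands: no listed objective, outcome or analysis uses the sheet, so the harm is to description and interpretation.

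Third, controls are not without contact. There is the day-7 call and the health questionnaire, and section 1 says subjects attend the clinic every week, whereas Table 1 shows no visit between baseline and day 14. Those statements need reconciling. Complaints may be volunteered at any such contact, but none is described as asking for them.

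Three stronger readings are tempting and are not supported:
- A reader might infer that the drop-out comparison is unfair. Drop-out can be seen in the same way in both arms at the day-15 visit; only its reasons may be documented unequally.
- A reader might infer that the sheet is the trial's only safety record and that the control count is zero by construction. The section numbers jump from 12 to 15, so an adverse-event section may exist outside the text shown, and controls can volunteer complaints.
- A reader might infer that a false significant difference is likely. That needs a high complaint rate, full capture in one arm and almost none in the other, and the protocol supplies none of these.

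**Conclusion.** The point holds in a limited form and is minor. In the text shown, problems during treatment are recorded prospectively in the juice arm only, while both arms share the diet and know their allocation. Problem frequencies from that sheet should not be compared between arms or read as effects of the juice. One-sided daily recording is a further difference between arms whose effect on adherence is possible but unknown.

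The size of any false difference is p(1-s), which cannot be fixed from the protocol. The illustrative range of 0 to 0.40 rests on an equal true rate in both arms, full capture by the sheet and assumed rates of 0.10 to 0.40. The drop-out count, the primary outcomes and the sample size are not affected.

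**What to change.** - Give both arms the same daily sheet for the 14 days, with the same question about any problem. Keep the time of juice consumption as an extra line for the juice arm only.
- Ask the same open question about problems in both arms at the day-7 telephone interview and at Visit 3.
- Record the reason for every withdrawal in both arms.

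The cost is one extra page for the 18 controls, one question at contacts that already take place, and a little more data entry. It changes no treatment and no planned analysis. It has to be in place before enrolment, because daily reports cannot be recovered afterwards. If controls are not given the sheet, the protocol should say that problem counts from it will be described for the juice arm only and not compared.
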